Study Design

Patients

The open-labeled trial is conducted at the Kaohsiung Veterans General Hospital, Kaohsiung Medical University Hospital and Kaohsiung Chang Gung Memorial Hospital in Taiwan in accordance with the principles of good clinical practice from the Declaration of Helsinki. The study protocol was approved by the Ethics Committees in each study center. All patients will be given written informed consent before participating in the study. Patients between the ages of 20 and 80 years with clinical symptoms of acid regurgitation, heart burn, or feeling of acidity in the stomach, who have Barrett's Esophagus proven by histology confirmation of esophageal metaplastic mucosa with length equal to or longer than 1 centimeter will be enrolled. Criteria for exclusions include (1) pregnancy, (2) coexistence of serious concomitant illness (for example, decompensated liver cirrhosis and uremia), (3) previous gastric surgery, (4) allergy to esomeprazole, (5) presence of dysplastic esophageal mucosa, and (6) equivocal endoscopic diagnosis of Barrett's esophagus (e.g., esophageal metaplastic mucosa less than 1 cm).

Study Design and Randomization

Eligible patients will be randomly assigned to receive either (1) on-demand PPI

therapy (40 mg of esomeprazole [Nexium, AstraZeneca, Sodertalje, Sweden] daily for 8 weeks, and then on-demand esomeprazole 40 mg daily if symptoms recurred.) or (2) continuous PPI therapy (40 mg of esomeprazole daily for 48 weeks). Randomization will be carried out with the use of a computer-generated list of random numbers. An independent staff member assigns the treatments according to consecutive numbers that are kept in sealed envelopes. The participants in the on-demand group will be instructed to take esomeprazole 40 mg daily for consecutive three days whenever reflux symptoms bothered them. If patients have obvious reflux symptoms soon after discontinuing PPI therapy twice or more, on-demand PPI treatment could be switched to continuous PPI use. In the continuous PPI therapy group, the participants take esomeprazole 40 mg daily no matter symptoms develop or not. All the participants are instructed to take esomeprazole 30 minutes before breakfast.

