A standardized data-collection form for medical history and demographic data will be obtained from each patient on enrollment, including age, sex, body mass index (BMI), medical histories, histories of smoking, alcohol, coffee and tea consumption. Smoking is defined as consumption of cigarettes 1 pack or more per week. Coffee or tea consumption is defined as drinking 1 cup or more per day.

Chinese GERDQ is a validated symptom questionnaire for the diagnosis and severity evaluation of gastroesophageal reflux disease. In the scoring system, the evaluated symptoms include acid regurgitation, heartburn and feeling of acidity in the stomach. The severity of symptoms in the questionnaire are graded on a five-point

Likert scale as follows: 1 (none; no symptoms); 2 (mild: symptoms can be easily ignored); 3 (moderate: awareness of symptoms but easily tolerated); 4 (severe: symptoms sufficient to cause an interference with normal activities); 5 (incapacitating: incapacitating symptoms with an inability to perform daily activities or work), and frequency of symptoms are graded as follows: 1 (none in the past year); 2 (less than once per month); 3 (\geq once per month); 4 (\geq once per week); 5 (\geq once daily). A cut-off score of ≥ 12 is used to make the diagnosis of symptomatic GERD.

Genotyping of CYP2C19

Blood sampling for genotyping of CYP2C19 will be carried out after endoscopy for the subjects who provides informed consent for genetic study. The *CYP2C19* genotype is determined using the polymerase chain reaction-restriction fragment length polymorphism (PCR-RFLP). Genotypes are classified into three groups: homEM (*CYP2C19*1/CYP2C19*1*); hetEM (*CYP2C19*1/CYP2C19*2*) and (*CYP2C19*1/CYP2C19*3*); PM (*CYP2C19*2/CYP2C19*2*, *CYP2C19*2/CYP2C19*3*, and *CYP2C19*3/CYP2C19*3*).

End Points

The primary outcome measures are (1) histological progression of metaplastic

esophageal epithelium at 48 weeks, and (2) total symptom days within the 48-week study period. The secondary outcome measure is total PPI consumption during the 48-week study period. Histological progression of metaplastic esophageal epithelium is defined as (1) progression from gastric metaplasia into intestinal metaplasia, low grade-dysplasia or high-grade dysplasia, or (2) progression from intestinal metaplasia into low-grade or high-grade dysplasia.

Statistics

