Our study is designed as a non-inferiority trial. Sample size was calculated from numbers needed to show that on-demand therapy is non-inferior to continuous therapy based on the proportion of patients who would discontinue the study prematurely because of unsatisfactory therapy. The hypothesis for sample size calculations are based on 94% on-demand therapy continuation rate and 92% continuous therapy continuation rate. On-demand therapy is defined as non-inferior to continuous therapy if the upper bound of the two-sided 90 % CI for the difference in proportions (on-demand minus continuous) is less than 10 %.

With a sample size of 78 patients in each treatment group, a one-sided test of proportions at the 5 % level had 90 % power to reject the hypothesis that on-demand therapy is inferior to continuous treatment. With an assumption of 10 % non-evaluable

patients and 10% non-eligible patients for randomization, it was calculated that 196 patients would be required in the initial enrollment to yield sufficient power.

Statistical analysis will be performed using the Statistical Program for Social Sciences (SPSS 19.0 for windows). Univariate analysis is performed by Student's t test for continuous variables and χ^2 test is used for categorical variables. $P < 0.05$ is considered statistically significant and all reported p values are two-sided.

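### The non-inferiority margin, sample size and 90% power belong to an outcome that is not a listed endpoint; neither listed primary outcome has a margin or power, so the plan cannot support non-inferiority on them.

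*Combined protocol and SAP*

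**What the plan says.** - **Design** (Statistics): "Our study is designed as a non-inferiority trial".
- **Outcome used for sizing** (Statistics): the calculation is "based on the proportion of patients who would discontinue the study prematurely because of unsatisfactory therapy", assuming "94% on-demand therapy continuation rate and 92% continuous therapy continuation rate".
- **Decision rule** (Statistics): on-demand therapy is non-inferior if "the upper bound of the two-sided 90 % CI for the difference in proportions (on-demand minus continuous) is less than 10" per cent. The sentence names no outcome but comes directly after the continuation rates.
- **Size and power** (Statistics): 78 per group, one-sided 5% level, 90% power, and 196 enrolled after two 10% allowances.
- **Endpoints** (End Points): "The primary outcome measures are (1) histological progression of metaplastic" epithelium at 48 weeks, and (2) total symptom days over the 48 weeks. "The secondary outcome measure is total PPI consumption during the 48-week study period". Discontinuation appears in neither list.
- **Tests** (Statistics): Student's t test for continuous variables and chi-square for categorical ones, with significance at P < 0.05; "all reported p values are two-sided".
- **Switching** (Study Design and Randomization): when reflux symptoms return soon after stopping PPI on two or more occasions, "on-demand PPI treatment could be switched to continuous PPI use".

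**The concern.** A non-inferiority conclusion needs a margin fixed in advance for the outcome on which the claim is made, and a sample size that gives known power against it. Here both exist for one outcome, and the trial names two different outcomes as primary. For those two, the plan supplies only tests whose null hypothesis is no difference. Failing to reject that null does not exclude a clinically important disadvantage, yet in a trial labelled non-inferiority a P value above 0.05 will readily be read that way. One of the primaries is progression of metaplasia, including to dysplasia, so false reassurance would matter. The plan also does not say whether one or both primaries must succeed.

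The outcome that was powered is itself incompletely defined. An on-demand patient whose symptoms keep returning may be moved to continuous PPI, and nothing says whether that counts as discontinuation because of unsatisfactory therapy. The continuous arm has no corresponding provision. If switches are not counted, dissatisfied on-demand patients can stay out of the event count.

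**Working it through.** **1. Reproducing the plan's figure.** Inputs from the Statistics section: continuation 94% and 92%, so discontinuation 6% (on-demand) and 8% (continuous); margin 10 points; one-sided 5% (z = 1.645); power 90% (z = 1.2816).

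n per group = (1.645 + 1.2816)² × (0.06×0.94 + 0.08×0.92) / (0.10 + 0.02)² = 8.564 × 0.130 / 0.0144 = 77.3, so 78.

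Power at 78: the standard error is √(0.130/78) = 0.0408, and Φ(0.12/0.0408 − 1.645) = 90.2%. Exact binomial enumeration with a Wald interval gives 90.6%. Enrolment: 78/0.80 = 97.5, rounded up to 98 per group, or 196. The arithmetic is sound and belongs to discontinuation.

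**2. Histological progression.** The documents give no rate, and no margin tied to this outcome. For illustration I borrow the 10-point margin and assume equal true rates p: power = Φ(0.10/√(2p(1−p)/78) − 1.645).

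| Assumed rate | Power at 78 per group | Exact enumeration | n per group for 90% |
|---|---|---|---|
| 2% | 99.8% | 98.8% | 34 |
| 5% | 88.9% | 88.8% | 82 |
| 10% | 66.9% | 67.6% | 155 |
| 20% | 46.7% | 47.2% | 275 |

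With an assumed 5-point margin, power at the same four rates is 72.1%, 41.6%, 27.3% and 19.4%.

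**3. What the planned chi-square test would show.** Suppose on-demand is truly 10 points worse on progression (assumed). The table gives exact probabilities at 78 per group, two-sided 5%, no continuity correction. The last column applies a 90% Wald interval and a 10-point margin.

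| On-demand vs continuous | Chi-square non-significant | Interval rule wrongly declares non-inferiority |
|---|---|---|
| 12% vs 2% | 25.4% | 7.5% |
| 15% vs 5% | 42.9% | 6.2% |
| 20% vs 10% | 57.3% | 5.6% |
| 30% vs 20% | 69.5% | 5.2% |

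**4. Total symptom days.** This is not a proportion, so the 10-point rule cannot apply. With no true difference and one-sided 5%, the smallest margin with 90% power at 78 per group is (1.645 + 1.2816) × √(2/78) = 0.469 SD. The plan states neither a margin nor an SD.

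**5. Switches counted as events.** The documents give no switch rate, so s below is an assumption: extra on-demand events added to the assumed 6%, against 8% on continuous therapy, margin 10 points. Power = Φ((0.12 − s)/√(V/78) − 1.645), where V = (0.06+s)(0.94−s) + 0.08×0.92; n per group = 8.564 × V/(0.12 − s)².

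| s (points) | Power at 78 per group | n per group for 90% |
|---|---|---|
| 0 | 90.2% | 78 |
| 2 | 74.4% | 127 |
| 5 | 44.0% | 300 |
| 10 | 10.4% | 4,454 |

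**The case against.** - **The rule might cover histology.** It speaks only of a difference in proportions, and progression is also a proportion for which an upper bound on on-demand minus continuous points the right way. This is a possible reading, but the rule follows directly from the discontinuation assumptions. Even if it were extended, no progression rate or power supports it, and it still cannot cover symptom days.
- **The tests are assigned by type of variable, not to the primaries by name.** True, but no other method is stated, so these are the tests the primaries would receive.
- **A switched patient stays in the study, so a literal reading says a switch is no event.** The sizing sentence does refer to leaving the study. The next sentence, however, refers to continuation of on-demand therapy, which a switched patient has not continued. The point is open and needs a stated answer. The power losses in step 5 rest on assumed switch rates with no overlap with the 6%; they show sensitivity and are not a forecast.
- **Power for histology may be adequate.** At low progression rates with a 10-point margin it would be. The defect is that the plan fixes neither the rate nor the margin, so no power can be claimed.
- **Demoting the declared primaries is the sponsor's choice.** This stands. The sponsor may instead set margins for them, on the conditions given in the fix.

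**Conclusion.** The concern holds and must be fixed. As written, the 90% power and the 10-point rule apply to an outcome outside the endpoint list, and the plan provides no valid route to non-inferiority on either declared primary. That conclusion comes from comparing the End Points and Statistics sections and rests on no assumed figure. The size of the consequence does rest on assumptions. Across the progression rates and margins tried, power at 78 per group runs from about 19% to above 99%. With a true 10-point disadvantage on progression, a non-significant chi-square result would occur between a quarter and about 70% of the time. The undefined handling of switches is an additional gap in the one outcome that was powered.

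**What to change.** **Non-inferiority claim.** List discontinuation because of unsatisfactory therapy as the single endpoint for the non-inferiority claim. Name it in the rule: the upper bound of the two-sided 90% CI for the difference in discontinuation proportions, on-demand minus continuous, must be below 10 points. State that the 90% power applies to this endpoint only.

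**Switches.** Reconcile the endpoint with the switching provision in Study Design and Randomization by stating, before data are seen, whether a switch counts as an event. Report the result with and without switches counted, and restate the power if they count. This concerns counting only and leaves the clinical provision to the sponsor.

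**Histological progression and total symptom days.** Report between-arm differences with confidence intervals, make no non-inferiority claim on them, and state that P ≥ 0.05 is not evidence of non-inferiority. No success rule across the two is then needed. If non-inferiority is to be claimed on them as well, fix a justified margin for each before data are seen, require all three endpoints to succeed (each at one-sided 5%, so no alpha split is needed), and restate power for each and jointly.

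**Cost.** An amendment to the endpoint and statistics wording, a narrower claim and less favourable power statements. No extra patients are needed for the basic route if switches do not count, or if lower power is accepted and disclosed. Holding 90% power with switches counted would need the numbers in step 5. Holding it for histology at a 10-point margin would need about 82, 155 or 275 per group at assumed rates of 5%, 10% or 20%.

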They are requested to complete a Chinese GERDQ on enrollment. The total score of GERD symptoms will be recorded. Each participant should complete diary cards during the study period. They return to the clinics for drug refills and evaluation of reflux symptoms every month. The participants are asked to hand in daily symptom records at each visit, and to report the number of esomeprazole tablets taken per 4-week period. Follow-up endoscopy with biopsy for esophageal mucosal metaplasia

will be performed at the end of 48 weeks.

Endoscopy

Endoscopy is performed on enrollment, and the esophagus is carefully evaluated.

Endoscopic suspected esophageal metaplasia (ESEM) is defined as a tongue-shaped projection of salmon-colored mucosa from the esophagogastric junction (the point where the proximal end of the gastric folds meets the tubular esophagus). All of the four quadrants of ESEM will be sampled every 2 cm. The Barrett's esophagus is defined as gastric or intestinal metaplastic change of distal esophageal epithelium confirmed by biopsy. The grade of Barrett's esophagus is scored according to the Prague C & M criteria. All subjects with biopsy-proven Barrett's esophagus will be further categorized into long-segment Barrett's esophagus and short-segment Barrett's esophagus. Long-segment Barrett's esophagus is defined as the maximal length of metaplastic columnar epithelium over distal esophagus equal to or more than 3 cm, and short-segment Barrett's esophagus is defined as the extension of columnar epithelium over distal esophagus less than 3 cm. Erosive esophagitis will be scored using the Los Angeles classification system. Hiatus hernia is defined as a distance between the esophagogastric junction and the diaphragmatic hiatus equal to or more than 1 cm.

H pylori examination

Two biopsy specimens are taken from the lesser curvature sites of the antrum, and another two from the corpus. They will be fixed in 10% buffered formalin, embedded in paraffin, and sectioned. The sections, 4- μ m thick, will be stained with a haematoxylin and eosin stain and a modified Giemsa stain to observe the presence of curved rod shape bacteria on the mucosal surface. Biopsy specimens will be assessed by histopathologists, who are blinded to patient status and the results of other laboratory tests.

Questionnaire

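### Both primary outcomes are to be compared with unadjusted tests, leaving unused the baseline metaplasia type and GERDQ score collected at enrolment: a loss of precision, not of validity

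*Combined protocol and SAP*

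**What the plan says.** The Statistics section states: "Univariate analysis is performed by" Student's t test for continuous data, with the chi-square test for categorical data. It does not link either test to a named outcome. The only other inferential methods in that section are a two-sided 90% confidence interval and a one-sided test of proportions. Both belong to the non-inferiority criterion on discontinuation for unsatisfactory therapy, which is not a primary outcome. The word univariate might hint at a later multivariable step, but none is described.

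The End Points section names two primary outcomes: histological progression at 48 weeks and total symptom days over 48 weeks. Progression means either "progression from gastric metaplasia into intestinal metaplasia, low grade-dysplasia or high-grade dysplasia" or "progression from intestinal metaplasia into low-grade or high-grade dysplasia".

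Both baseline variables exist before treatment. The Endoscopy section places an endoscopy at enrolment and has Barrett's esophagus "defined as gastric or intestinal metaplastic change of distal esophageal epithelium confirmed by biopsy". Under Study Design and Randomization, patients complete the Chinese GERDQ on enrolment, and "The total score of GERD symptoms will be recorded". On allocation the same section says "Randomization will be carried out with the use of a computer-generated list of random numbers", with no stratification factor.

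**The concern.** The first primary outcome pools two different events. A gastric-type patient progresses on reaching intestinal metaplasia or dysplasia; an intestinal-type patient progresses only on reaching dysplasia. Starting type therefore fixes which routes to an event are open to each patient, and it is likely to be prognostic. A crude chi-square test ignores it. Because no stratum is stated for randomisation, the design does not balance type between the arms either.

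GERDQ grades the severity and frequency of reflux symptoms, so it is a natural baseline covariate for symptom days. The planned t test ignores it.

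Two things are at stake: wider confidence intervals than the collected data need give, and a between-arm difference that can partly reflect a chance excess of one metaplasia type in one arm. If the investigators adjust only after seeing such an imbalance, in an open-label trial, the choice will look data-driven.

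**Working it through.** **The plan's own figure.** With continuation rates of 94% and 92%, a margin of 10 points, one-sided 5% and 90% power:

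n = (0.94×0.06 + 0.92×0.08) × (1.645 + 1.282)² / 0.12² = 77.3, so 78 per arm.

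The total follows as 78/0.80 = 97.5, so 98 per arm and 196 in all. Both figures reproduce with an unadjusted formula. They concern discontinuation, so nothing below changes them; 78 per arm is used only as the number evaluable.

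**Assumptions.** The documents give no progression rates, gastric share or GERDQ correlation. Assumed ranges:
- share of gastric-type patients, g: 0.3–0.7
- progression in gastric-type patients, pG: 0.10–0.40
- progression in intestinal-type patients, pI: 0.02–0.05
- correlation of baseline GERDQ with symptom days, r: 0.2–0.5

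**1. Chance imbalance in type.** The SD of the between-arm difference in gastric share is √(2g(1−g)/78), which is 0.073 at g = 0.3 or 0.7 and 0.080 at g = 0.5. The probability of a gap of 10 points or more is 17–21% by the normal approximation. It is 19–23% by exact binomial calculation, taking 8 or more patients of 78.

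**2. Effect of a 10-point gap.** The shift in the crude risk difference is 0.10 × (pG − pI).
- Smallest: 0.10 × (0.10 − 0.05) = 0.5 points.
- Largest: 0.10 × (0.40 − 0.02) = 3.8 points.

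With p̄ = g·pG + (1−g)·pI, the crude SE is √(2p̄(1−p̄)/78) = 0.033–0.073. Over the scenarios the shift is 0.1–0.7 SE.

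**3. Variance saved by stratifying.** Cut = 1 − [g·pG(1−pG) + (1−g)·pI(1−pI)] / [p̄(1−p̄)].

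Example at g = 0.3, pG = 0.40, pI = 0.02: p̄ = 0.134, and the cut is 1 − 0.0857/0.1160 = 26%.

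| Gastric progression | Variance cut | SE cut |
|---|---|---|
| 10% | 1–3% | 0.3–1.6% |
| 20% | 4–10% | 2–5% |
| 40% | 12–26% | 6–14% |

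Simulation of the Mantel-Haenszel risk difference in 18 scenarios gave variance cuts from about 0 to 26%.

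**4. Validity of the crude test of progression.** Simulated two-sided type I error was 4.8–5.4% overall. Given an imbalance of exactly 8 patients in type, it was 5.0–7.6%.

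**5. Sparse strata.** With 39 intestinal-type patients per arm at 2%, the chance of no events in a given arm is 0.98^39 = 45.5%, and in both arms 0.98^78 = 20.7%. The adjusted method must cope with this.

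**6. Symptom days.** Adjusting for GERDQ multiplies the variance by 1 − r².
- r = 0.2: factor 0.96, worth 78/0.96 = 81 per arm.
- r = 0.3: factor 0.91, worth 78/0.91 = 86 per arm.
- r = 0.5: factor 0.75, worth 78/0.75 = 104 per arm.

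In 20,000 simulated null trials at r = 0.5, with normally distributed data, the t test and the covariate-adjusted test both rejected 5.0% of the time. In the 13% of trials with a baseline imbalance beyond 1.5 SE, the t test rejected 13% and the adjusted test 5%.

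**The case against.** An unadjusted comparison after randomisation is legitimate, and its standard error already allows for chance imbalance. The raised error rates in steps 4 and 6 come from selecting unlucky trials out of a procedure whose overall error is correct. This stands: the point is about precision and interpretation, and no error in the planned tests is claimed.

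The gain depends wholly on assumed rates. At 10% gastric progression it is negligible. The 26% figure needs 40% of gastric-type patients to progress within 48 weeks against 2% of intestinal-type patients. That stands too, and the gain could be nil. The GERDQ correlation is equally unsupported: the frequency item looks back as far as a year before enrolment, while symptom days are counted on treatment, and both arms take daily esomeprazole for the first 8 weeks. A correlation near 0.2 would be worth only about three patients per arm.

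Baseline type does enter the definition of the outcome. It does not enter the comparison as a stratum or covariate, which is where precision is gained.

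Adjustment also leaves open how either primary outcome relates to the non-inferiority claim, since the only margin concerns discontinuation. That is a separate gap and does not argue against using the baseline data.

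Finally, the variance estimator matters. In simulation the Mantel-Haenszel risk difference held 5.0–5.4% with the Sato variance, but a stratum-by-stratum binomial variance gave 5.4–6.0%. This objection is met by naming the estimator.

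**Conclusion.** The concern holds, and the change should be made. The plan describes no analysis of either primary outcome that uses baseline metaplasia type as a stratum or GERDQ score as a covariate. The crude tests are not made invalid by this. Under the stated assumptions, the variance given up is about 1–26% for progression and 4–25% for symptom days. The progression gain is material if gastric-type patients progress much more often than intestinal-type patients, and small or nil if progression is rare in both. Roughly one trial in five would show a gap in type of 10 points or more, moving the crude risk difference by 0.5–3.8 points. Confidence in the size is moderate, because none of these rates or correlations is in the documents.

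**What to change.** Add to the Statistics section, before outcome data are examined by arm:

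- **Histological progression (primary analysis):** a Mantel-Haenszel risk difference with confidence interval, stratified by baseline metaplasia type (gastric or intestinal), using the Sato variance. This tolerates strata with few or no events. Avoid unpenalised logistic regression, which can fail there.
- **Total symptom days (primary analysis):** a linear model with arm and baseline GERDQ total score.
- **Supportive:** the crude chi-square and t tests.
- **Reporting:** progression by arm within baseline type, so that readers can separate gastric-type from intestinal-type progression.

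The cost is wording in the analysis plan. Both covariates are already obtained at enrolment, and no extra patients, visits or measurements are needed. The 78 per arm is unaffected.
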